6.8 Duration of Participation

The total duration of participation for subjects in this study will be up to 6 weeks (initial screening visit through follow-up visit).

7. ASSESSMENT OF EFFICACY

7.1 Continuous Recording of Blood Pressure

BP will be recorded, using ABPM, on three 25-hour periods during the trial: Day -1 to Day 0, Day 6 to Day 7, and Day 13 to Day 14. Subjects deemed to be too hypertensive to continue in the study after 7 days of study drug administration, will only have one 25-hour ABPM measurement following randomization: Day 6 to Day 7. Those treated with study drugs for 14 days, will have two 25-hour ABPM measurements following randomization: Day 6 to Day 7 and Day 13 to Day 14.

Subjects will have the ABPM fitted to their upper extremity with the greater BP (See Section 8.3). They will be instructed not to remove the monitor and will be shown how to refit it, in case it becomes dislodged.

ABPM measurements will be recorded as described in Appendix D. The subject's baseline systolic and diastolic BP values will be the SBP_{day} , SBP_{night} , SBP_{24h} , DBP_{day} , DBP_{night} , and DBP_{24h} obtained during the Day -1 to Day 0 ABPM measurement.

Although BP will be manually taken during clinic visits as part of the safety assessments (Section 8.3), it is the values obtained from the ABPM that will constitute the official BP values for all efficacy determinations and calculations for this study.

7.2 Body Weight

Body weight will be measured at Screening, Day 0, Day 7, and at Day 14. The weight measurements will be made using a calibrated scale with the subject wearing only underwear and a light gown.

The body weight measurements will serve a dual function as both a secondary efficacy endpoint and a secondary assessment for safety. Further, the measurement of the change in body weight from baseline to the end of treatment will serve as an indirect measure of renal function.

7.3 Renal Function

Renal function as measured by estimated creatinine clearance is a secondary efficacy assessment of this trial. Creatinine clearance will be estimated at the initial screening visit, Day 0, Day 7, and Day 14. Creatinine clearance will be estimated by the Cockcroft-Gault equation as follows:

$$\text{estimated creatinine clearance} = (140 - \text{age}) \times \text{body weight (kg)} / 72 \times P_{Cr} \text{ (mg/dL)}$$

multiply by 0.85 for women

8. ASSESSMENT OF SAFETY

Safety will be assessed primarily based on reported TEAEs. Secondary safety assessments will include the following: physical examination, body weight, vital signs, orthostatic hypotension evaluations, ECG, hematology, serum chemistry, and urinalysis. Refer to Appendix A (Schedule of Events) for the timing of these safety assessments.

8.1 Adverse Events

8.1.1 Definitions

8.1.1.1 Adverse Event

An AE is defined in the Guideline for Good Clinical Practice E6(R1) (ICH Harmonised Tripartite Guideline, dated June 10, 1996) as follows:

Any untoward medical occurrence in a subject or clinical investigation subject administered a pharmaceutical product and which does not necessarily have a causal relationship with this treatment. An AE can therefore be any unfavourable and unintended sign (including an abnormal laboratory finding), symptom, or disease temporally associated with the use of a medicinal (investigational) product, whether or not related to the medicinal (investigational) product.

Any untoward medical occurrence that initiates or worsens after completion of the initial screening visit procedures and before administration of the first dose of study drugs will be recorded as a PTAE.

Any untoward medical occurrence that initiates or worsens after the first dose of study drugs and within 14 days of the last dose of study drugs will be recorded as a TEAE.

8.1.1.2 Serious Adverse Event

An SAE is defined in the Guideline for Good Clinical Practice E6(R1) (ICH Harmonised Tripartite Guideline, dated June 10, 1996) as follows:

Any untoward medical occurrence that at any dose:

- results in death,
- is life-threatening,
- requires inpatient hospitalization or prolongation of existing hospitalization,
- results in persistent or significant disability/incapacity, or
- is a congenital anomaly/birth defect.

PTAEs meeting the above definition for SAE (disregarding the “at any dose” part of the definition) will be considered serious PTAEs.

TEAEs meeting the above definition for SAE will be considered serious TEAEs

8.1.2 Severity of Adverse Events

The severity of PTAEs and TEAEs will be graded according to WHO Toxicity Criteria (Appendix C).

The severity of PTAEs and TEAEs not classified by the above referenced toxicity grading scale will be categorized using the following definitions:

Mild: discomfort noted, but no disruption of normal daily activity

Moderate: discomfort noted of sufficient severity to reduce or adversely affect normal activity

Severe: incapacitating, with inability to work or perform normal daily activity

8.1.3 Relationship of Treatment Emergent Adverse Events to the Study Drug

The Investigator should assess the relationship of TEAEs to the study drug and classify as one of the following:

1. **Adverse reaction:** AE that is caused by the study drug.
2. **Suspected adverse reaction:** AEs for which there is a reasonable possibility that the drug caused the AE. Reasonable possibility means there is evidence to suggest a causal relationship between the drug and the AE. A suspected adverse reaction implies a lesser degree of certainty about causality than adverse reaction. Examples of the types of evidence that would suggest reasonable possibility of a causal relationship between the drug and the AE are as follows:
 - A single occurrence of an event that is uncommon and known to be strongly associated with drug exposure (e.g., angioedema, hepatic injury, Stevens-Johnson Syndrome)
 - One or more occurrences of an event that is not commonly associated with drug exposure, but is otherwise uncommon in the population exposed to the drug (e.g., tendon rupture)
 - An aggregate analysis of specific events observed in a clinical trial (such as known consequences of the underlying disease or condition under investigation or other events that commonly occur in the study population independent of drug therapy) that indicates those events occur more frequently in the drug treatment group than in a concurrent or historical control group

3. **Unrelated:** AE for which there is evidence that the AE definitely has an etiology other than the study drug.

8.1.4 Expectedness of Adverse Events

An unexpected AE is one for which the nature or severity of the event is not consistent with the applicable study drug information (i.e., the most current version of the IB, the current product labeling for amlodipine tablets, and the current product labeling for celecoxib capsules) or listed in this protocol.

This study will enroll older subjects with existing hypertension. To that end, PTAEs and TEAEs can be expected due to the subjects' age and underlying conditions. These include: hypertension, hypertensive crisis, myocardial infarction, congestive heart failure, stroke both hemorrhagic and ischemic, any adult forms of cancer, and gastrointestinal ulcerations with complications including hemorrhage and perforation.

By definition, PTAEs initiate prior to administration of the first dose of study drugs, and thus a comparison against study drug specific risk information is inappropriate for determining expectedness of PTAEs. Thus, only AEs that can be expected due to subject age and underlying conditions are relevant for the expectedness determination for PTAEs.

8.1.5 Monitoring of Adverse Events

Monitoring for PTAEs will begin upon completion of the initial screening visit procedures and will continue through the 9 to 13 days of washout, the final screening visit on Day -1, and the baseline procedures on Day 0 (i.e., prior to the administration of the first dose of study drugs). Any untoward medical occurrence that initiates or worsens after completion of the initial screening visit procedures and before administration of the first dose of study drugs will be recorded as a PTAE.

Monitoring for TEAEs will begin immediately following administration of the first dose of study drugs and will continue throughout the study. Any untoward medical occurrence that initiates or worsens after the first dose of study drugs and within 14 days of the last dose of study drugs will be recorded as a TEAE.

Subjects will be instructed to report all PTAEs and TEAEs experienced during the study, and subjects will be assessed for the occurrence of PTAEs and TEAEs throughout the study. In order to avoid bias in eliciting AEs, subjects will be asked general, non-leading questions such as "How are you feeling?"

All study drug-related TEAEs (adverse reaction or suspected adverse reaction per the definitions in Section 8.1.3) will be followed until resolution or stabilization of the event. This may require additional clinical assessments and laboratory tests.

8.1.6 Routine Reporting of Adverse Events

PTAEs and TEAEs, whether or not associated with study drug administration, will be recorded on the AE form of the CRF and will be submitted to the Sponsor at regularly scheduled intervals.

The information to be entered in the CRF will include:

1. Medical diagnosis of the event in standard medical terminology (if a medical diagnosis cannot be determined, a description of each sign or symptom characterizing the event);
2. Date of onset of any new AE or the worsening of a previously observed AE. For the days when the subject is in the clinic, the time (based on a 24-hour clock) of onset should be recorded if available;
3. Date of resolution of the event (or confirmation ongoing). For the days when the subject is in the clinic, the time (based on a 24-hour clock) of resolution should be recorded if available;
4. Whether the event is serious (per definition in Section 8.1.1.2), and if so, the reason it is considered serious;
5. Severity of AE (per definitions in Section 8.1.2);
6. Assessment of the relationship of the AE to the study drug (per definitions in Section 8.1.3). Relationship assessments will only be made for TEAEs;
7. Whether the event is expected (per definition in Section 8.1.4);
8. Action taken in treating the AE (including concomitant medications or therapies administered) and/or change in study drug administration or dose (including whether the Study Drug was temporarily interrupted or discontinued);
9. Outcome of AE (recovered/resolved, recovered/resolved with sequelae, not recovered/not resolved, fatal, or unknown). Fatal should only be used when death is possibly related to the AE. If an outcome for an AE is not available at the time of the initial report, follow-up will proceed until an outcome is known or followed up to the final study visit. Any subject with a possible study drug-related TEAE at the final study visit will be followed until resolution or stabilization of the event. Further, any serious TEAE, whether or not related to study drugs that occurs within 14 days following the last dose of study drugs will be followed until resolution or stabilization of the event.

8.1.7 Reporting of Serious Adverse Events, Including Death

Serious PTAEs or serious TEAEs, including death due to any cause, which occur during this study or within 14 days following the last dose of the study drugs, whether or not related to the administration of study drugs, must be reported by the Investigator or other Investigational Site personnel directly to the Pharmacovigilance Officer at PM Clinical LTD by fax **within 24 hours of learning of the event**. The Pharmacovigilance Officer will forward this information to the Medical Monitor for review. The contact information for the Pharmacovigilance Officer is provided below.

Pharmacovigilance Officer: [name] [name]

[contact]

[contact]

[contact]

SAE Forms will be provided by the Sponsor or Sponsor designated CRO. If all information is not known at the time of initial reporting, an initial report should still be made. In the event there is a question as to whether the experience is serious, the information should be forwarded to the Pharmacovigilance Officer, who will then forward the information on to the Medical Monitor for review. The Investigator is responsible for following up on completion of the SAE Form. The Investigator will submit substantiating data in hard copy form, such as diagnostic test reports and progress notes, to the Pharmacovigilance Officer. In the case of fatality, autopsy reports will be furnished to the Pharmacovigilance Officer as soon as available.

In the event of a medical emergency or a serious TEAE that is unexpected (as defined in Section 8.1.4) and possibly related to the study drug(s) (i.e., an adverse reaction or suspected adverse reaction as defined in Section 8.1.3), the blind will be broken for the subject that experiences the event. An emergency code break envelope for each subject will be provided to each Investigational Site and also to the Pharmacovigilance Officer. In the event that the Investigational Site personnel need to unblind the study treatment and cannot access the relevant code break envelope at the site, they can contact the Pharmacovigilance Officer at any time.

The following information about the subject and the reported SAE will be collected on the SAE Form:

1. Subject identification including subject number, initials, and date of birth;
2. Randomization number (only for serious TEAE);
3. Date of first dose of study drugs and details of administration, including study drug names (including labeled strength and manufacturer), lot number, expiration date, and dose (only for serious TEAEs). If the serious TEAE does not require breaking of the blind, certain study drug specific details will not be available to enter in the initial SAE Form, but will be reported in the SAE Form updates;
4. Date of last dose of study drugs (i.e., prior to onset of SAE) and details of administration, including study drug names (including labeled strength and manufacturer), lot number, expiration date, and dose (only for serious TEAEs). If the serious TEAE does not require breaking of the blind, certain study drug specific details will not be available to enter in the initial SAE Form, but will be reported in the SAE Form updates;
5. Medical diagnosis of the event in standard medical terminology (if a medical diagnosis cannot be determined, a description of each sign or symptom characterizing the event);
6. Date of onset of the event. For the days when the subject is in the clinic, the time (based on a 24-hour clock) of onset should be recorded if available;

7. Date of resolution of the event (or confirmation ongoing). For the days when the subject is in the clinic, the time (based on a 24-hour clock) of resolution should be recorded if available;
8. Severity of the event (see Section 8.1.2);
9. Assessment of the attributability of the event to the study drug (see Section 8.1.3) (only for serious TEAE);
10. Why event is considered serious (per definition in Section 8.1.1.2);
11. Whether the event is expected (see Section 8.1.4);
12. Action taken in treating the event and/or change in study drug administration or dose (including concomitant medications or therapies administered, whether hospitalization or prolongation of hospitalization was required, diagnostic procedures performed, whether the study drug was temporarily interrupted or discontinued, and whether the subject was discontinued from the study);
13. Outcome of AE (recovered/resolved, recovered/resolved with sequelae, not recovered/not resolved, fatal, or unknown). Fatal should only be used when death is possibly related to the AE. If an outcome is not available at the time of the initial report, follow-up will proceed until resolution or stabilization of the event and an updated SAE Form will be issued.
14. All concomitant medications (including doses, routes, regimens, and indications) taken within 30 days prior to the initial screening visit through the point of onset of the event;
15. Pertinent laboratory data;
16. Medical history.

The Investigator and the Medical Monitor will review each SAE report and evaluate the relationship of the adverse experience to study drug and to underlying disease. Based on the Investigator's and Medical Monitor's assessment of the adverse experience, a decision will be made concerning the need for further action. The primary consideration governing further action is whether new findings affect the safety of subjects participating in the clinical trial. If the discovery of a new adverse experience related to the study drug raises concern over the safety of continued administration of study drug, the Sponsor will take immediate steps to notify the regulatory authorities.

Further action that may be required includes the following:

1. Alteration of existing research by modification of the protocol;
2. Discontinuation or suspension of the study;

3. Alteration of the informed consent process by modification of the existing consent form and informing current study participants of new findings;
4. Modification of previously identified expected adverse experiences to include adverse experiences newly identified as study medication-related.

Any SAE that is determined by the Sponsor to be reportable to the Food and Drug Administration (FDA) as an Investigational New Drug application (IND) Safety Report [as defined in 21 Code of Federal Regulations (CFR) 312.32] will be reported to FDA by the Sponsor within the specified time frame. All IND Safety Reports will also be promptly provided to the Investigator for submission to his or her IRB/IEC. Similarly, any SAE that is determined by the Sponsor to require expedited reporting to other regulatory authorities will be reported to the appropriate authorities by the Sponsor designated CRO within the specified time frames, and will be provided to the Investigator for submission to his or her IRB/IEC.

8.2 Physical Examination

A comprehensive physical examination will be performed at the initial screening visit and on Day 14. The comprehensive physical examination will include the following organ or body system assessments: skin; head, eyes, ears, nose, and throat; thyroid; lungs; cardiovascular; abdomen (liver, spleen); lymph nodes; and extremities, as well as an abbreviated neurological exam.

A targeted physical examination will be performed at baseline (Day 0) and at the Day 7 and Day 28 visit. This examination will specifically target the cardiovascular system and will include vital signs, plus an examination of the extremities to check for the presence of edema, as well as an examination to document any other evidence of a cardiovascular problem. Any areas of concern from the medical history or noted on the prior physical examination or indicated by subject symptoms or other findings as determined by the Investigator or designee may also be examined.

8.3 Vital Signs

Vital sign measurements (BP, pulse rate, respiration rate, and oral body temperature) will be collected on the days and times noted in the Schedule of Events (Appendix A). Vital signs will be taken with the subject in the sitting position after 5 minutes of rest, except for at the initial screening visit, where vital signs will be taken with the subject in the supine position after at least 10 minutes of rest with minimal interaction.

Measurements of BP made when subjects are at the Investigational Site as part of their clinic visits will be made using the standard American Heart Association criteria (Chobanian, 2003). This will require the following technique be utilized:

1. Clinic visit BP measurements will be taken at the initial screening visit, in the morning on Days 0, 7, and 14, and at the follow-up visit (Day 28). On Day 0, the BP measurements will be taken in the morning prior to the first dose of study drugs. On Day 7, the subject will self-administer their study drugs at home prior to coming to the clinic, and therefore, the BP measurements will be taken after the subject has taken their daily dose of study drugs;

2. A determination will be made as to which upper extremity has the greater BP;
3. Prior to taking the subject's BP, the subject will rest in the sitting position for a period of 5 minutes, except for at the initial Screening visit, where BP measurements will be taken with the subject in the supine position after at least 10 minutes of rest with minimal interaction;
4. At the completion of the rest period, three readings will be taken. There will be a one minute interval between each measurement;
5. The subject's recorded BP will be an average of the three recordings taken over approximately three minutes.
6. At the initial screening visit (Day -10 to -14), three readings will be taken on each arm, as described. The averages for each arm will be calculated. The arm with the higher average systolic BP will be used for all further BP measurements including ABPM measurements.

The continuous recording of BP by ABPM (Section 7.1) at Day -1 to Day 0, Day 6 to Day 7, and Day 13 to Day 14, will serve a dual function as both the official BP values for all efficacy determinations and calculations and an additional BP assessment for safety.

8.4 Orthostatic Hypotension Evaluations

Orthostatic hypotension will be evaluated at baseline (Day 0), Day 7, and Day 14.

For this determination, the subject will be placed supine for 5 minutes. At the end of that time a manual BP will be assayed three times. The average of these three will be used as the baseline value. The subject will then be asked to stand vertically and two manual BPs will be obtained: the first will be one minute after standing and the second will be three minutes after standing. Orthostatic hypotension will be defined as a decrease in systolic BP of > 25 mmHg from baseline in either of the readings, or a decrease in diastolic BP of > 15 mmHg in either of the readings compared to the baseline average.

In addition to these quantitative measurements, specific comparisons in reported AE rates for terms associated with hypotension will be made. These events will include dizziness, falls, light-headedness, and vertigo.

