6. Collect the ABPM and download the systolic and diastolic BP values obtained by the ABPM and incorporate into the subject's medical record and CRF;
7. Orthostatic hypotension evaluation (see Section 8.4);
8. 12-lead ECG;

9. Blood sampling for hematology and serum chemistry (see Appendix B for list of tests);
10. Collection of urine for urinalysis (see Appendix B for list of tests);
11. Urine pregnancy test for WCBP only;
12. Blood sample will be collected at 24 hours \pm 1 hour post-dose for measurement of amlodipine concentrations. Only subjects enrolled at Investigational Sites that have UV-shielded lights will participate in the PK blood collections. Due to the design of the trial (randomized, double-blind, placebo-controlled), this blood sample will be collected and analyzed for all participating subjects, regardless of whether they are in a treatment arm that receives amlodipine.

Following the Day 14 evaluations, the following procedures will be performed:

1. Instruct subjects to resume taking their prescribed BP medication as directed by the study doctor or general practitioner;
2. Instruct subjects to continue to not take any NSAIDs or investigational drugs for the remainder of the study (through Day 28);
3. For WCBP: Instruct subjects to continue to use adequate contraceptive methods for the remainder of the study (through Day 28);
4. Subjects will be provided back their diary and instructed to record any concomitant medications taken between visits;
5. Subjects will be instructed to return to the clinic in 14 days (Day 28) for final study visit (follow-up visit), and to bring the completed diary to the visit.

6.7 Study Day 28

Subjects will return to clinic on Day 28 for their final study visit (follow-up visit). The following evaluations will be performed:

1. Solicit history of TEAEs since last visit;
2. Review diary for details of concomitant medications taken since last visit;
3. Targeted physical examination (see Section 8.2);
4. Vital signs (BP, pulse rate, respiration rate, and oral body temperature).

For subjects whose study drug is discontinued at Day 7, this follow up-visit will still occur on Day 28 (i.e., these subjects will return to the clinic for both the Day 14 and Day 28 visits).

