12.3 Pharmacokinetics

After oral administration of therapeutic doses of NORVASC, absorption produces peak plasma concentrations between 6 and 12 hours. Absolute bioavailability has been estimated to be between 64 and 90%. The bioavailability of NORVASC is not altered by the presence of food.

Amlodipine is extensively (about 90%) converted to inactive metabolites via hepatic metabolism with 10% of the parent compound and 60% of the metabolites excreted in the urine. *Ex vivo* studies have shown that approximately 93% of the circulating drug is bound to plasma proteins in hypertensive patients. Elimination from the plasma is biphasic with a terminal elimination half-life of about 30–50 hours. Steady-state plasma levels of amlodipine are reached after 7 to 8 days of consecutive daily dosing.

The pharmacokinetics of amlodipine are not significantly influenced by renal impairment. Patients with renal failure may therefore receive the usual initial dose.

Elderly patients and patients with hepatic insufficiency have decreased clearance of amlodipine with a resulting increase in AUC of approximately 40–60%, and a lower initial dose may be required. A similar increase in AUC was observed in patients with moderate to severe heart failure.

Drug interactions

In vitro data indicate that amlodipine has no effect on the human plasma protein binding of digoxin, phenytoin, warfarin, and indomethacin.

Impact of other drugs on amlodipine

Co-administered cimetidine, magnesium-and aluminum hydroxide antacids, sildenafil, and grapefruit juice have no impact on the exposure to amlodipine.

CYP3A inhibitors: Co-administration of a 180 mg daily dose of diltiazem with 5 mg amlodipine in elderly hypertensive patients resulted in a 60% increase in amlodipine systemic exposure. Erythromycin co-administration in healthy volunteers did not significantly change amlodipine systemic exposure. However, strong inhibitors of CYP3A (e.g., itraconazole, clarithromycin) may increase the plasma concentrations of amlodipine to a greater extent [see *Drug Interactions (7.1)*].

Impact of amlodipine on other drugs

Co-administered amlodipine does not affect the exposure to atorvastatin, digoxin, ethanol and the warfarin prothrombin response time.

Simvastatin: Co-administration of multiple doses of 10 mg of amlodipine with 80 mg simvastatin resulted in a 77% increase in exposure to simvastatin compared to simvastatin alone [see *Drug Interactions (7.2)*].

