#### **b. Other PTs of interest**

The protocol specified a comparison of AE rates for terms associated with hypotension, defined as dizziness, falls, light-headedness, and vertigo. The definition will be changed to TEAEs with PTs of orthostatic hypotension, fall, dizziness, dizziness postural, and vertigo. The use of PTs and the addition of orthostatic hypotension to the list provides a more precise and comprehensive analysis, as well as allows a direct comparison to a similar analysis conducted for the prior trial (KIT-302-03-01). Note, light-headedness is coded under dizziness as a PT.

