### **Other PTs of interest**

Other PTs of interest will be defined as any TEAE with a PT of orthostatic hypotension, fall, dizziness, dizziness postural, or vertigo.

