Similar tabular summaries will be produced for each of the following: treatment emergent SAEs, ADRs, oedema events, other PTs of interest, treatment emergent UAEs, TEAEs leading to discontinuation, PTAEs, PTAEs leading to discontinuation, and pre-treatment SAEs. In the case of the latter two, the summaries will not be produced if there are no PTAEs leading to discontinuation or pre-treatment SAEs, respectively. For the ADR summary, if an ADR is reported more than once for a given subject, the worst-case attribution will be presented in the summary table.

A comparison of TEAE rates between the amlodipine + celecoxib and amlodipine + placebo arms will be performed using an exact logistic regression model with the TEAE ("1"=At least one TEAE occurred for the patient; "0"=otherwise) as dependent variable and treatment (amlodipine + celecoxib and amlodipine + placebo) as fixed effects. The probability modeled will be TEAE="1". The number of patients and the number of patients considered in the model will be provided. The exact odds ratio of the fixed effects will be calculated (amlodipine + celecoxib and amlodipine + placebo) with the relative 95% CI and p-value.

The same model will be repeated by considering treatment-emergent SAE (“1”=At least one treatment-emergent SAE occurred for the patient; “0”=otherwise) as dependent variable, with the caveat that if no treatment-emergent SAEs are reported the table will not be produced.

The rates of oedema events between the amlodipine + celecoxib arm and the amlodipine + placebo arm will be compared using an exact logistic regression and reporting the odds ratio. Oedema event (1 = at least one TEAE with PT of oedema, oedema peripheral, peripheral swelling, swelling, or joint swelling occurring for the subject; 0 = otherwise) will be the dependent variable, and treatment (amlodipine + celecoxib and amlodipine + placebo) will be the fixed effects.

The Fisher’s exact test will be run to compare the number of oedema events that occurred while on treatment (Day 0 to Day 14+1) and post-treatment (>Day 14+1) between treatment arms 1 and 2 (amlodipine + celecoxib and amlodipine + placebo).

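### The arm comparison of hypotension-type adverse events pools on-treatment events with events in the two weeks after dosing, when subjects have been told to resume their own antihypertensive; an on/post-treatment split should be added.

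*Protocol*

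**What the plan says.** Protocol 8.4 defines a measured orthostatic test at Days 0, 7 and 14 and adds an adverse-event comparison: "In addition to these quantitative measurements, specific comparisons in reported AE rates for terms associated with hypotension will be made". It gives that comparison no time window.

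SAP 1.3.9b revises the list of terms: "The definition will be changed to TEAEs with PTs of orthostatic hypotension, fall, dizziness, dizziness postural, and vertigo". SAP 6.4 repeats it as the analysis variable: "Other PTs of interest will be defined as any TEAE with a PT of orthostatic hypotension, fall, dizziness, dizziness postural, or vertigo". Neither limits onset to the treatment period, so the general TEAE rule applies. Under Protocol 8.1.1.1 an event starting or worsening after the first dose and "within 14 days of the last dose of study drugs will be recorded as a TEAE". SAP 7.9 tabulates this category by arm and tests group differences by chi-square or Fisher's exact test.

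Study drug is taken on Days 0 to 13 (Protocol 5.3). After the Day 14 evaluations the site is to do the following (Protocol 6.6): "Instruct subjects to resume taking their prescribed BP medication as directed by the study doctor or general practitioner".

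For oedema, SAP 1.3.9a and 7.9 plan an additional Fisher test of arms 1 and 2 on the events "that occurred while on treatment (Day 0 to Day 14+1) and post-treatment".

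**The concern.** This is the plan's adverse-event check on whether adding celecoxib to amlodipine changes hypotension-type symptoms. A resumed antihypertensive can itself plausibly produce dizziness, falls or orthostatic hypotension, so the post-treatment part of the window answers a different question from the on-treatment part. If the two amlodipine arms have similar post-treatment risks, pooling adds a common background to both and moves the ratio towards 1. A null result could then be read as more reassuring than it is.

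Elsewhere the SAP keeps off-drug time apart. It leaves Day 28 out of the clinic blood pressure ANCOVA because subjects have by then been off study drug for 14 days (1.3.9h), compares orthostatic pressures only on the change to Day 14 (1.3.9i), and gives oedema an on/post-treatment split. The hypotension terms get no such separation.

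**Working it through.** The plan states no event rate, power or window share for this comparison, so there is no figure to reproduce. The window can be counted from the documents. The dilution can only be illustrated with assumed rates.

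**1. Share of the window off study drug**

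- Completer, last dose Day 13: the window is Day 0 to Day 13 + 14 = Day 27, or 28 calendar days. Days 14 to 27 carry no dose: 14/28 = 50%.
- By elapsed time, allowing 24 h of cover after the Day 13 dose: 13/27 = 48%.
- By the SAP's oedema cut (post-treatment is after Day 14+1, i.e. Days 16 to 27): 12/28 = 43%.
- Subject stopped at Day 7 after taking that day's dose: the window is Days 0 to 21, or 22 days, and 14/22 = 64% is off drug. A fixed Day 15 cut would label Days 8 to 15 (8 of those 14 days) as on treatment.

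**2. Residual drug**

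Appendix F (12.3) describes amlodipine elimination as "biphasic with a terminal elimination half-life of about" 30 to 50 h. The fraction left 72 h after the last dose is 2^(−72/30) = 0.19 to 2^(−72/50) = 0.37. Five half-lives take 5 × 30/24 = 6.3 to 5 × 50/24 = 10.4 days. For celecoxib (about 11 h, Appendix G 12.3) five half-lives take 5 × 11/24 = 2.3 days. Most of the exposure contrast between arms 1 and 2 is thus gone within two to three days, while residual amlodipine overlaps with the resumed drug for about a week or more.

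**3. Effect of pooling**

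Let p1 and p2 be the on-treatment risks in the two amlodipine arms and q a post-treatment risk common to both (an assumption). Then P = 1 − (1 − p)(1 − q) in each arm, the pooled risk ratio is P1/P2, and the risk difference is P1 − P2 = (1 − q)(p1 − p2). The arm size is 105 × 3/7 = 45. Power is exact for a two-sided Fisher test at 0.05 (the safety alpha in SAP 7.3), arm against arm.

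| On-treatment risks (assumed) | q (assumed) | Pooled risks | Ratio | Difference (points) | Fisher power |
|---|---|---|---|---|---|
| 20% v 5% | 0 | 20.0 v 5.0 | 4.00 | 15.0 | 48% |
| | 2.5% | 22.0 v 7.4 | 2.98 | 14.6 | 40% |
| | 5% | 24.0 v 9.75 | 2.46 | 14.25 | 34% |
| | 10% | 28.0 v 14.5 | 1.93 | 13.5 | 25% |
| 15% v 5% | 0 | 15.0 v 5.0 | 3.00 | 10.0 | 23% |
| | 10% | 23.5 v 14.5 | 1.62 | 9.0 | 12% |
| 10% v 5% | 0 | 10.0 v 5.0 | 2.00 | 5.0 | 6% |
| | 10% | 19.0 v 14.5 | 1.31 | 4.5 | 5% |
| 6.8% v 3.4% | 0 | 6.8 v 3.4 | 2.00 | 3.4 | 2% |
| | 10% | 16.1 v 13.1 | 1.23 | 3.1 | 4% |

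The last scenario starts from the only dizziness rates in the documents: 3.4% on amlodipine 10 mg against 1.5% on placebo (Appendix F 6.1), and 2.0% on celecoxib against 1.7% on placebo (Appendix G 6.1). It takes 3.4% for one arm and doubles it for the other. These rates cover one of the five terms and come from other populations, so they are a guide only.

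**The case against.** **The oedema precedent is narrower than it looks.** A reader might infer that the SAP restricts oedema to on-treatment events and so treats hypotension differently in its main comparison. It does not. An oedema event is also any TEAE (SAP 6.4), the exact logistic regression of arms 1 and 2 uses the full window (7.9), and the Day 14+1 split is an extra test. Oedema also has a stated mechanistic hypothesis (Protocol Section 1); none is given for dizziness or falls. This stands. The precedent supports adding a split, not replacing the full-window comparison.

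**The scale and the rates matter.** No ratio is planned for this category, only counts, percentages and a test, and SAP 7.9 does not say that the test is arm 1 against arm 2. On the difference scale pooling costs little: 15.0 points become 13.5 even at a 10% post-treatment risk. The marked loss of power appears only at on-treatment risks well above the label rates. At 10% v 5% or 6.8% v 3.4% the test has 2% to 6% power whichever window is used. This stands too.

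**Late events are not simply non-study-drug events.** With 19% to 37% of amlodipine left at three days, early post-treatment events may still reflect randomised treatment, and some are background. Against arm 3, residual amlodipine on top of a resumed drug is a real consequence of having been randomised to amlodipine, not a bias. This argues against discarding post-treatment events, but it does not argue for leaving the periods unseparated.

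**Much is available already.** Orthostatic pressures are compared on the change to Day 14, each TEAE is listed with its onset date and relationship, and medications are classified by date. The PT definition was chosen to allow comparison with the prior trial (SAP 1.3.9b). Listings, however, do not give a reader the two-period comparison.

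**Conclusion.** The point holds as a modest one. The hypotension-term comparison uses a window of which about half, for completers, lies after the last dose and, from Day 14, after the instruction to resume an antihypertensive. It therefore mixes two exposure periods that the SAP separates for oedema.

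A reader might go further and conclude that a celecoxib effect on hypotension is being hidden. The documents do not support that. They give no event rates for this comparison, and the pull towards a ratio of 1 depends on similar post-treatment risks in arms 1 and 2, which is plausible but not shown. The risk difference barely changes, and the test is weak with or without the split. The measured orthostatic evaluations, the primary endpoint and the sample size are untouched. What the split gains is interpretability: a reader could tell events on study drug from events after it.

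**What to change.** In SAP 1.3.9b and 7.9, add for these five terms the split and the arm 1 versus arm 2 Fisher test already planned for oedema: on treatment (Day 0 to Day 14+1) against post-treatment.

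- Set the cut from the actual last dose. Day 15 is two days after a completer's Day 13 dose, so last dose + 2 days reproduces the SAP's cut and also handles early stoppers.
- Flag each post-treatment event by whether the subject had resumed blood pressure medication at onset.
- Keep the full-TEAE comparison alongside. It preserves comparability with the prior trial and retains events under residual amlodipine.
- SAP v4.0 is dated after unblinding (SAP 1.5), so label the split post hoc if it is added now.

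The cost is SAP wording and one more table. Onset dates, last-dose dates and concomitant medications are already collected, and trial conduct does not change. The downside is few events in each period, so the table will be mainly descriptive.
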